**Table 2-2 Dose and treatment schedule – Consolidation**

Treatment	Dose, route and frequency (based on 28-day cycles)
Cytarabine	1-3 g/m  every 12 h on days 1, 3, 5 x up to 4 cycles based on age and per investigator discretion
Midostaurin	50 mg (two 25 mg capsules) twice a day by mouth on days 8-28

**Table 2-3 Dose and treatment schedule – Maintenance**

Treatment	Dose, route and frequency (based on 28-day cycles)
Midostaurin	50 mg (two 25 mg capsules) twice a day by mouth on days 1-28

## 2.5.2 Study treatment and tolerability

### Study treatment

Duration of exposure (days), actual cumulative dose and actual dose intensity will be summarized by period and overall for each of the study drugs: midostaurin, daunorubicin and idarubicin for the safety set. Duration of exposure (days), actual cumulative dose and actual dose intensity will be summarized also by cycle. The number of patients with midostaurin dose changes, interruptions and permanent discontinuations will be presented by age category and overall, along with reasons for the dose change/interruption/permanent discontinuation.

Duration of midostaurin treatment exposure (days) will also be categorized and summarized by period and overall for the safety set using the following intervals:

- ≤ 20; >20; >40; >60; >120; >180; >240; >300; >360

Duration of study treatment exposure (days) will be summarized by period and overall for the safety set using the following intervals:

- ≤ 28; >28; >56; >84; >112; >196; >280; >364; >448; >532

Duration include the rest/recovery days between cycles and will be derived as the following:

Last intake of any study treatment component – first intake of any study treatment component +1

If there are more than 10 patients in each regimen exposure will be further summarized by regimen (“7+3” and “5+2”).

Data will be listed for all patients in the safety set.

### **Tolerability**

Tolerability of midostaurin will be evaluated in terms of dose reductions or dose interruptions due to an AE.

#### **2.5.3 Prior, concomitant and post therapies**

Medications and significant non-drug therapies prior to and after the start of the study treatment will be coded according to the world health organization (WHO) Drug Reference List and summarized by anatomical therapeutic chemical (ATC) classification and preferred term.

A summary table and listing for prior antineoplastic therapies will be provided for the full analysis set.

Summary tables for concomitant medications and concomitant non-drug therapies by treatment period and overall for the full analysis set will be provided. Prior, concomitant and post study treatment medications and non-drug therapies will be listed for the safety set. Records outside of on-treatment period will be flagged.

#### **2.5.4 Protocol deviations**

Protocol deviations will be listed for all screened patients. In addition, the number (%) of protocol deviations with COVID-19 relationship will be presented by type of deviation for all enrolled subjects.

### **2.6 Analysis of the primary objective**

#### **2.6.1 Primary endpoint**

The analysis of the primary endpoint is described in [Section 2.8](#).

#### **2.6.2 Statistical hypothesis, model, and method of analysis**

Not applicable.

#### **2.6.3 Handling of missing values/censoring/discontinuations**

See [Section 2.8](#).

#### **2.6.4 Supportive analyses**

Not applicable.

## **2.7 Analysis of the secondary objectives**

### **2.7.1 Secondary endpoints**

The secondary objectives in this study are to assess the clinical efficacy of midostaurin in combination with chemotherapy regimens in induction and consolidation and the clinical efficacy of midostaurin in maintenance phase.

Clinical efficacy rate will be presented for the FAS. All assessments before the last available on-treatment assessment will be included. Listings will include all data and will be based on the FAS. Records outside of on-treatment period will be flagged. For patients who discontinued prior to the first efficacy assessment, the response will be reported as ‘unknown’.

Clinical efficacy rate is defined as the proportion of patients with complete remission (CR) or complete remission with incomplete hematologic recovery (CRi) as per local review. The CR and CRi are defined by the national comprehensive cancer network (NCCN) guidelines version 1.2017 for AML.

Clinical efficacy rate and its 95% confidence interval will be presented by period (induction, consolidation and maintenance) and overall as described in [Section 2.1.1](#). The best overall response will be analyzed in each period and overall. If there are more than 10 patients in each regimen and age category, the clinical efficacy rate will be further summarized by regimen (“7+3” and “5+2”) and age category (e.g. <=60, >60 years and/or <= 60 / >60 to <=70 / > 70 years old) and by sex.

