4.3 Definition of end of study

The study will end around 18 to 25 months after LPFV depending on number of cycles and recovery durations. Study treatment will be provided until disease progression, death, unacceptable toxicities, physician's decision, subject/guardian's decision, protocol deviation, study termination by sponsor, lost to follow-up, technical problems, pregnancy, patient withdrew consent or until the end of study, whichever event occurs first. Patients will be contacted for safety evaluations. All patients must have safety evaluations for 30 days, after the last dose of study treatment except if consent was withdrawn. Patients who present CR/CRI may be eligible for transplant. Patients who undergo SCT will have midostaurin discontinued prior to conditioning for transplantation, and will be removed from the study following completion of scheduled safety monitoring.

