7.1.4.1 Induction phase

Newly diagnosed AML patients will receive “7+3” or “5+2” induction therapy with cytarabine and daunorubicin (or idarubicin) as defined by NCCN treatment guidelines ([NCCN Guidelines v1.2017](#)). Enrolled patients will subsequently receive oral midostaurin 50 mg (two 25 mg capsules) twice a day on days 8-28 (see [Table 6-1](#)). Patients should take their doses at approximately the same time each day, and approximately 12 hours should elapse between the morning and evening doses. Each daily dose should be given with food and a glass of water (~240 mL). Patients should be instructed to swallow capsules whole and not chew capsules. If vomiting occurs, no re-dosing is allowed prior to the next scheduled dose.

A switch between regimens is not allowed.

Refer to [Table 6-1](#) for Induction treatment schedule.

Patients who achieved a CR/CRI after the first cycle may continue with the consolidation phase, all other patients may get a second induction cycle as per investigator’s discretion.

Second induction cycle

For patients requiring a second induction cycle, treatment will begin at least 3 days and no later than 42 calendar days after completing midostaurin. The treatment regimen must also adhere to the guidelines specified above for the first induction. Please refer to [Section 7.2.1](#).

Patients who have achieved a CR/CRI after the second cycle may continue with the consolidation phase; all other patients should be removed from protocol.

Patients may start consolidation treatment at least 3 days and no later than 42 calendar days after the last midostaurin dose of induction.

An end phase disposition will be completed prior the C1D1 of the consolidation phase.

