7.1.4.2 Consolidation phase

Patients who achieved a CR/CRI after either one or two induction cycles will receive consolidation therapy with cytarabine as defined by NCCN treatment guidelines plus subsequent midostaurin during each cycle. Patients will receive up to four cycles of consolidation therapy. Fewer cycles are accepted as per investigator’s discretion.

Each consolidation cycle is 28 days treatment. It is recommended that subsequent cycle start at least 3 days after the previous cycle is completed and no later than 70 calendar days from the start of the first cycle of consolidation. For the other consolidation cycles a recovery periods of 21 days maximum will be applied. Refer to [Table 6-2](#) for consolidation treatment schedule.

An end phase disposition will be completed prior the C1D1 of the maintenance phase.

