7.2 Assessment types

7.2.1 Efficacy assessments

Induction therapy

FLT3 mutated patients will receive induction therapy (cytarabine with anthracycline (idarubicin or daunorubicin) (for details refer to [Section 6.1.1](#)) sequentially followed by midostaurin.

In the first Induction phase, a bone marrow aspiration will be performed in all patients on Day 21-28 (according to local standard of care) to determine the need for a second induction cycle. If the marrow aspirate is inadequate to make a determination, repeat the bone marrow assessment within one week.

If the Day 21-28 (according to local standard of care) bone marrow aspiration reveals <5% blasts in a cellular marrow (> 20%), then a bone marrow aspiration must be performed within one week after recovery of ANC $\geq 1\,000/\mu\text{L}$ and platelets $\geq 100\,000/\mu\text{L}$ to document complete remission. Patients in CR will proceed to consolidation therapy. Patients with CRI will proceed to consolidation therapy as per investigator discretion.

If the Day 21-28(according to local standard of care) bone marrow aspiration reveals $\geq 5\%$ leukemic blasts in a cellular marrow (> 20%) a second induction will be given.

Second Induction therapy (if applicable)

For patients requiring a second induction, treatment will begin at least 3 days after completing midostaurin.

Bone marrow aspiration will be performed within one week after recovery of ANC $\geq 1000/\mu\text{L}$ and platelets $\geq 100,000/\mu\text{L}$ to assess for response.

Patients in CR will proceed to consolidation therapy. Patients who have residual AML at this time after a second remission induction should be removed from protocol therapy. Patients with CRI will proceed to consolidation therapy as per investigator's discretion.

Consolidation therapy (up to four cycles per investigator's discretion)

Based upon the superior results reported for AML patients less than 60 years old with normal karyotypes in prospective clinical trials ([Farag et al 2005](#)) and RATIFY, who achieve a CR/CRI after induction will receive further therapy with midostaurin. Patients will receive up to four cycles of consolidation therapy. Each consolidation cycle is four weeks in duration, and should begin within two weeks following hematologic recovery (ANC $\geq 1000/\mu\text{L}$, platelet count $\geq 100,000/\mu\text{L}$), but not sooner than 31 days from the beginning of the previous cycle. If a

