#### 2.1.1 General definitions

The overall observation period is divided into the following **mutually exclusive** periods:

1. **Pre-treatment:** from day of patient's informed consent to the day before first dose of midostaurin

2. **On-treatment:** from start date of midostaurin to last date of study treatment + 30 days.

Further details provided in [Section 2.1.3](#).

On-treatment includes 3 mutually exclusive periods:

- a. **Induction** period: From day of first dose of midostaurin to the day before start of consolidation period (i.e. end of induction phase plus any rest/recovery days).  
Up to 2 cycles (28 days of treatment/cycle and a recovery period)
- b. **Consolidation** period: From day of first dose of study treatment in consolidation phase to the day before start of maintenance (i.e. end of consolidation phase plus any rest/recovery days).  
Up to 4 cycles (28 days of treatment/cycle and a recovery period)
- c. **Maintenance** period: From day of first dose of midostaurin in the maintenance phase to the date of last dose of midostaurin + 30 days.  
Up to 12 cycles (28 days of treatment/cycle)

It is noted that if a patient permanently discontinues study treatment during any of these periods, on-treatment is considered until the date of last dose of study treatment + 30 days (unless patient withdraws study informed consent or dies before then, then it is till the withdrawal/death date)

3. **Post-treatment:** from last date of study treatment + 31 days to end of study

Each period will contain all patients who entered that period (incl. withdrawal, drop-outs etc.)

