#### **2.1.3 On-treatment assessment/event**

The definition of on-treatment is given below, depending on the context.

For safety summary tables (over the entire duration of the study) an on-treatment AE is defined as any AE reported in the following time interval (including the lower and upper limits):

- <date of first administration of midostaurin; date of last administration of study treatment + 30 days>

This corresponds to the definition of treatment-emergent AEs given in the protocol, i.e. AEs which are newly reported or worsening from baseline.

An on-treatment assessment is defined as any assessment performed after the date of first administration of midostaurin (except for assessments specified to be collected post-dose on that day), i.e. assessments performed in the following time interval (including the lower and upper limits):

- <date of first administration of midostaurin + 1; date of last administration of study treatment + 30 days>

For patients whose last date of study treatment is missing, on-treatment assessments/events include any assessment/event present in the database occurring after the start date of study treatment.

Listings will contain all data, flagging assessments/events outside of the on-treatment period where applicable.

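### Read literally, the CR/CRi rule leaves out the last on-treatment assessment; separately, a response first found more than 30 days after the last dose counts only if the patient continues treatment

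*SAP*

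**What the plan says.** SAP 2.7.1 defines the clinical efficacy rate as the share of the FAS with CR or CRi by local review. It is given with a 95% confidence interval by period and overall, using best response. The rule on eligible assessments is: "All assessments before the last available on-treatment assessment will be included". Patients who stopped before their first efficacy assessment are classed as unknown. SAP 2.7.3, on missing values, is marked not applicable.

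SAP 2.1.3 sets the on-treatment window for assessments as "<date of first administration of midostaurin + 1; date of last administration of study treatment + 30 days>". Under SAP 2.1.1 the induction period runs "From day of first dose of midostaurin to the day before start of consolidation period (i.e. end of induction phase plus any rest/recovery days"), and the consolidation period is built the same way. For a patient who stops permanently in any period, "on-treatment is considered until the date of last dose of study treatment + 30 days".

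The protocol allows longer intervals between phases:
- Section 7.1.4.1: "Patients may start consolidation treatment at least 3 days and no later than 42 calendar days after the last midostaurin dose of induction".
- Section 7.1.4.2: the next cycle should begin "no later than 70 calendar days from the start of the first cycle of consolidation".
- Section 7.2.1: if the Day 21-28 marrow of first induction shows under 5% blasts in a cellular marrow, "then a bone marrow aspiration must be performed within one week after recovery of ANC" and platelets. No calendar limit is given.
- Section 4.3: "Patients who present CR/CRI may be eligible for transplant". Such patients stop midostaurin before conditioning and leave the study after safety monitoring.
- Section 7.1.5 and Table 7-1: an End of Treatment visit includes marrow and CR/CRi.

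Protocol 10.5 calculates the rate on the FAS with neither restriction. SAP section 4 records no change from the protocol.

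**The concern.** One sentence decides which marrows can make a patient a responder, and its literal meaning is probably not the intended one. A programmer who follows it would discard the last response assessment of every patient, including patients who have only one.

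The on-treatment cut adds a second problem. It is a safety convention tied to the last dose, applied here to a disease outcome. Two patients with the same marrow result at the same interval after the same last dose can be classified differently because one of them later received more study treatment. Response status would then depend on what happened after the response was documented.

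**Working it through.** **Plan's own figure.** The documents give no figure for the response rule. The only design figure is the chance of seeing at least one AE of 1% incidence in 300 patients: 1 - 0.99^300 = 0.9510. It reproduces, but has no bearing here.

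**Step 1: the literal rule.** With k on-treatment response assessments, the sentence uses k - 1.

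| Pattern | Result under the literal rule |
|---|---|
| One assessment, CR/CRi | Nothing left to use; the 'unknown' rule does not cover it either |
| No response first, CR/CRi only at the last | Not a responder |
| CR/CRi earlier, End of Treatment assessment later | Response kept |
| Stops in consolidation, only marrow in that phase is at End of Treatment | No usable consolidation assessment; an earlier induction CR/CRi still counts overall |

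The last pattern can arise because, after the marrow before the first consolidation cycle, marrow during consolidation is at the investigator's discretion (Protocol 7.2.1, Table 7-1). The unplanned-visit table in SAP 2.1.5 also gives End of Treatment its own row, tied to no period.

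**Step 2: the 30-day window against the protocol intervals** (last midostaurin dose on cycle day 28).
- After induction: window ends 28 + 30 = day 58; latest start of consolidation 28 + 42 = day 70; gap 70 - 58 = 12 days.
- After consolidation cycle 1: 70 - 28 = 42 days allowed; gap 42 - 30 = 12 days.
- After other consolidation cycles: at most 21 days of recovery; no gap.
- Before maintenance: at most 28 days; no gap.
- Midostaurin stopped early in induction, on day 8, 14 or 21: window ends on day 38, 44 or 51, always after the Day 21-28 marrow.

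**Step 3: two patients, same result.** Both take the last induction dose on day 28, and both have a first CR on day 63.
- Patient A starts consolidation on day 66. The last study treatment date moves later, day 63 lies in the induction period, and the CR counts.
- Patient B stops. The window closed on day 58, so the CR is listed and flagged but does not enter the rate.

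A patient who stops after consolidation cycle 1 had to be in CR/CRi to enter consolidation, so the 30-day gap there affects the consolidation rate, not the overall rate.

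**Step 4: size.** The number affected is not in the documents. For illustration only, assume N = 300 and a true rate of 65%, that is 195 responders. Reported rate = 195 x (1 - share lost), rounded to whole patients, / 300.

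| Share of responders lost (assumed) | Responders counted | Reported rate |
|---|---|---|
| 0% | 195 | 65.0% (95% CI 59.3-70.4) |
| 2% | 191 | 63.7% |
| 5% | 185 | 61.7% |
| 10% | 176 | 58.7% |
| 20% | 156 | 52.0% |

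The nearest figure in the protocol is from RATIFY (section 1.2.1.2.2): CR 58.9% within 60 days against 65.0% for all induction CRs, a difference of 6.1 points.

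**The case against.** The strongest reply is that the sentence is a drafting slip. Best response per period and overall, together with an 'unknown' class limited to patients with no assessment, makes sense only if the last assessment is used. That reading is the more natural one and is accepted here as the likely intent. It does not settle the matter, because neither rule says which assessments are eligible.

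On the window, four replies carry weight.
- The 42 days is the latest start of the next phase or cycle, not a statement that recovery takes that long. It applies only after induction and consolidation cycle 1.
- The endpoint includes CRi, which does not need full count recovery, so many patients awaiting counts would already be responders. This narrows the gap without closing it: Protocol 7.2.1 requires at least 7 transfusion-free days for CR and CRi alike, so a patient still being transfused meets neither.
- The End of Treatment visit is due as soon as possible after stopping, and will often fall within 30 days. It can fall later when the decision not to continue is made during recovery.
- Planned follow-up after stopping is 30 days of safety evaluation, so some late responses may never be recorded. That part would be a limit of data collection, not of the SAP rule.

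A reader might go further and infer that about 6 points of response are being lost, chiefly in patients sent to transplant. The documents do not support this. The RATIFY difference concerns CR alone and may include second-induction CRs, whose window here would close later. It also counts patients who went on to consolidation, and they lose nothing under this rule. More than half of RATIFY patients were transplanted, but no transplant number is given for this trial, and response normally comes before the transplant decision.

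**Conclusion.** The point holds in two limited parts. First, the sentence in SAP 2.7.1 literally excludes the last on-treatment response assessment. It costs a response only where that assessment is the only one showing CR/CRi in the period or overall, and only if the sentence is programmed as written. Second, patients who stop permanently after induction or consolidation cycle 1, with CR/CRi first documented in that period more than 30 days after the last dose, are treated differently from patients who continue. The gap is at most 12 days.

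Both effects can only lower the CR/CRi rate. Their size cannot be derived from the documents: the table above rests on assumed losses, and RATIFY is a loose indication at best. The endpoint is secondary and descriptive, no hypothesis is tested, and the listings still show late results. The primary safety analysis and the sample size are unaffected. Correction is still warranted, because this is the only efficacy endpoint and the restriction is neither in the protocol nor declared in SAP section 4.

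**What to change.** 1. Replace the sentence in SAP 2.7.1 with: 'All response assessments up to and including the last available one, including the End of Treatment assessment, and before any transplant conditioning or other anti-leukemic therapy, will be included.'
2. Assign the End of Treatment assessment to the period in which treatment stopped, even if it falls more than 30 days after the last dose.
3. Leave the 30-day AE window as it is.
4. Declare the change in SAP section 4. The latest SAP version is dated after database lock, so also show the rate under the 30-day on-treatment cut, with the last assessment included, so that readers can see what the wider window adds.

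The cost is two short rules, a programming change and one extra presentation of the rate. The response window will differ from the AE window and needs a footnote. The documents do not show that start dates of conditioning or new therapy are collected beyond the 30-day follow-up. The team should check this and state how a missing date is handled.

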## Document History – Changes compared to previous final version of SAP

Date	Time point	Reason for update	Outcome for update	Section and title impacted (Current)
22-Aug-2017	Prior to FPFV	N/A – Initial version	N/A	N/A
14-Jan-2020	Prior to database lock	Rules to select one assessment among several assessments in the same visit	Selection of assessment to analyze among multiple values in the same visit	2.1.5
		Time windows for unplanned visits	Time windows to assign unplanned visits in scheduled ones	
		Added rules to assign patients to 7+3 and 5+2 groups	Patients who do not have exactly 7+3 or 5+2 are assigned	2.1.8
		Category/Value missing	Added treatment exposure category “>28”. Cardiac imaging changed “>” to “>_” for 20	2.4.2 2.8.4.2
		Change in CSR template	Concomitant medications will be analyzed with FAS instead of SAF	2.4.3
		Clinical efficacy response derivation and subgroup analyses	Selection of best response among several assessment in the same period. Response analyzed by sex	2.6.1
		AEs by subgroup	AEs to be analyzed by age category	2.8.1
		Resource utilization updated to CRF	Updated with variables only included in CRF	2.13.3
		Additional details on imputation rules	Derivation rules updated	6.1
		BUN/Urea imputation rules	To impute BUN or Urea missing values	6.2
26-Jun-2020	Study treatment exposure	Rules od study treatment exposure clarified.		2.1.1
		Analysis set	All enrolled subjects added	2.2
	Subgroups analyses added : type of induction drugs		Efficacy and safety outputs provided by Idarubicin and Daunorubicin.	2.3
	Age subgroups		<= 60 vs. >60 instead of <60 vs. >=60	2.3 and 2.4.2

Date	Time point	Reason for update	Outcome for update	Section and title impacted (Current)
		Efficacy	If patient discontinued prior to first efficacy assessment then 'unknown' is assigned as best response	2.7.1
15-Jun-2021	Prior to database lock	PD	The number (%) of protocol deviations with COVID-19 relationship will be presented by type of deviation for all enrolled subjects.	2.5.4
09-Nov-2021	Post to database lock	Subgroups analysis amended for a new agesubgroup/category.	Included the following age subgroup/category: <= 60 / >60 to <=70 / > 70 years old	2.3, 2.4.2, 2.5.2 and 2.7.1
<hr/> 
FPFV: First patient first visit
 <hr/>				

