### **2.4 Patient disposition, demographics and other baseline characteristics**

#### **2.4.1 Patient disposition**

Disposition data will be listed and summarized descriptively by screening and period (induction, consolidation and maintenance) for the FAS.

Summaries will also include the number of patients who did not receive any dose of study treatment, having received at least one dose of study treatment, treatment completed as per protocol criteria or treatment permanently discontinued with reason, as reported in the dose administration record eCRF pages.

Informed consent and inclusion/exclusion criteria data will be listed. Screening data for screen failure patients will be listed.

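### Maintenance CR/CRi is scored as best response among patients who entered in CR/CRi, so it does not show whether remission was kept

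*SAP*

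**What the plan says.** SAP Section 2.7.1 sets the reporting: "Clinical efficacy rate and its 95% confidence interval will be presented by period (induction, consolidation and maintenance) and overall as described in" Section 2.1.1. It then states "The best overall response will be analyzed in each period and overall". The SAP document history (14-Jan-2020 entry) describes the derivation as "Selection of best response among several assessment in the same period". On which assessments count, Section 2.7.1 says "All assessments before the last available on-treatment assessment will be included".

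SAP Section 2.1.1 defines the maintenance period as "From day of first dose of midostaurin in the maintenance phase to the date of last dose of midostaurin + 30 days", with "Up to 12 cycles (28 days of treatment/cycle"), and adds "Each period will contain all patients who entered that period (incl. withdrawal, drop-outs etc".

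The protocol makes remission the condition for entering maintenance in Sections 7.1.4 and 7.1.4.3 and under the maintenance heading of Section 7.2.1. Section 7.2.1 and Table 7-1 schedule a marrow before the first maintenance cycle and every 3 months after that, and Table 7-1 also schedules one at end of treatment. Section 7.2.1 defines relapse. Section 7.1.5 lists progressive disease as a withdrawal reason and explains that it covers relapse. SAP Section 2.4.1 reports this: "Disposition data will be listed and summarized descriptively by screening and period (induction, consolidation and maintenance) for the FAS".

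**The concern.** A best-response rate suits a phase in which patients start without remission and may gain it, as in induction. In maintenance every entrant is already in remission, and the open question is who stays there. Protocol Section 2.3 gives that as the purpose: to act on residual blasts after chemotherapy and so possibly prolong OS and DFS. Best response over the period cannot answer it. The secondary objective names maintenance efficacy, and a high percentage with a confidence interval is easily read as evidence of it.

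The inclusion rule is a separate drafting fault. Taken at its word, it excludes the last on-treatment assessment, which is the one that shows status at the end. It can also exclude a patient's only CR/CRi. One example is a patient whose induction marrow shows CR and who then leaves for transplant. This fault can therefore affect any period, including induction.

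**Working it through.** **No planned figure to reproduce.** Neither document gives an expected maintenance CR/CRi rate.

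**Logic**

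1. Entrants are in CR/CRi (Protocol 7.1.4, 7.1.4.3, 7.2.1). The exception in 7.1.4.3 concerns incomplete consolidation and does not say that CR/CRi is waived.
2. One in-period CR/CRi fixes the patient as a responder (SAP 2.7.1 and document history).
3. A later relapse or death in the period therefore changes the numerator by 0. This holds whether the denominator is the FAS (SAP 2.7.1) or the patients who entered the period (SAP 2.1.1). With the FAS, the rate is also capped at entrants divided by FAS.
4. The rule in SAP 2.1.5 of taking the assessment closest to the target date works within a visit or cycle window. It does not replace best response over the period.
5. No relapse rate, remission duration, DFS or last-status analysis appears in the visible SAP text.

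**Illustration of size**

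Inputs:

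- Midostaurin-arm medians from the earlier phase III trial (Protocol 1.2.1.2.2): remission duration censored at transplant, 20.27 months; DFS, 26.7 months; DFS counting all induction CRs, 28.1 months; remission duration not censored at transplant, 61.0 months.
- Length of maintenance: T = 12 × 28 / 30.4375 = 11.04 months, using the SAP 2.1.4 definition of a month.
- Assumptions: constant hazard; every entrant assessed; first in-period marrow at 3 months; entry marrow not counted.

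Formulas: h = ln 2 / median and S(t) = exp(−h·t). Best response is S(3), still in remission at the end is S(11.04), and the gap is the difference.

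For the last-status comparison, let a proportion q stop for other reasons over maintenance while in CR/CRi, with c = −ln(1 − q) / 11.04. Such patients succeed under both rules. The gap is then exp(−3(h + c)) × h/(h + c) × [1 − exp(−8.04(h + c))], where 8.04 = 11.04 − 3.

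Worked case, median 20.27:

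- h = 0.6931 / 20.27 = 0.0342; S(3) = 0.9025; S(11.04) = 0.6856; gap = 0.217.
- With q = 10%, c = 0.00954; gap = 0.877 × 0.782 × 0.2965 = 0.203.

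| Median (months) | S(3) | S(11.04) | Gap, all followed (points) | Gap, q = 10% / 30% / 50% (points) |
|---|---|---|---|---|
| 20.27 | 0.9025 | 0.6856 | 22 | 20 / 17 / 14 |
| 26.7 | 0.9251 | 0.7508 | 17 | 16 / 14 / 11 |
| 28.1 | 0.9287 | 0.7616 | 17 | 16 / 13 / 11 |
| 61.0 | 0.9665 | 0.8821 | 8 | 8 / 7 / 6 |

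Of patients in remission at 3 months, 1 − exp(−8.04h) = 24%, 19%, 18% and 9% have a later event that best response does not register. Moving the first marrow to 84 days (2.76 months) gives a gap of 9 to 22 points with full follow-up.

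**The case against.** **Relapse is already reported.** This is partly right. Disposition by period will show patients who stopped for progressive disease, which in maintenance effectively means relapse, and the listings contain all response data. A reader might infer that the plan hides relapse; it does not. What is missing is a labelled efficacy estimate with a confidence interval. SAP Section 1 also places table shells and derivations in separate documents, so handling of the entry marrow and the denominator may be specified there.

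**The rate must be 100%.** A reader might infer this, but the documents do not support it in general. A patient who relapses, dies or stops before any in-period CR/CRi is not a maintenance responder. The rate among entrants is about 100% only if the entry marrow is dated C1D1 and counted in maintenance. The SAP 2.1.5 window for unplanned visits includes that date, but the SAP does not settle the question.

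**The illustration is weak.** This stands. The medians run from CR, not from maintenance entry, and entrants have already kept remission through consolidation. DFS also counts deaths without relapse. Protocol Section 2.3 reports quick relapse after maintenance stopped, which points to a smaller gap within the phase. Against that, the earlier trial's patients were aged 18 to under 60 (Protocol 1.2.1.2.2), while this trial has no upper age limit. The full-follow-up range also does not match a last-status measure, which is why the second range is given.

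**A last-status rate would not prove a maintenance effect either.** This is correct. With one arm and selected entrants, it describes durability without attributing it to midostaurin.

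**The stakes are limited.** Also correct: no hypothesis is tested, the primary objective is safety, and the protocol itself chose CR/CRi for this phase.

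**Conclusion.** The point stands for maintenance. The planned rate ignores any relapse that follows one in-period CR/CRi, so it cannot describe whether remission was kept. This follows from the entry condition and the scoring rule and needs no numerical assumption.

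The size is illustrative: 8 to 22 points if all event-free entrants are followed for 12 cycles, and about 6 to 20 points against last in-period status if an assumed 10% to 50% stop for other reasons. Both ranges rest on a constant hazard and borrowed medians, and the true gap could be smaller or larger.

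In consolidation the same logic applies, but marrows after the one before C1D1 are optional (Protocol 7.2.1). Best and last response may largely coincide there, and no gap is claimed. Best-response scoring is appropriate for induction, although the literal inclusion rule could remove a CR/CRi there too.

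The harm is possible misreading of a descriptive secondary result. It should be fixed, but it does not touch the primary safety objective.

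**What to change.** - Keep the planned best-response rates. Label the maintenance and consolidation rates as conditional on CR/CRi at entry.
- Add one supplementary maintenance table: among all FAS patients who entered maintenance, the proportion in CR/CRi at the last in-period assessment, with a 95% confidence interval.
- Count relapse or death in the period as failure. Keep patients with no in-period assessment in the denominator as non-responders, and also show them separately.
- Keep patients who leave for transplant in remission in the denominator with their last in-period status. Show them separately where the collected procedure data identify them.
- State that the entry marrow is not a response in the phase it opens.
- Reword the inclusion rule in SAP 2.7.1 so that the last on-treatment assessment is itself included.
- State that the single-arm rate describes durability and does not attribute it to midostaurin.
- Record the changes in the document history and SAP Section 4 as made after database lock.

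Cost: SAP wording and one table. No new assessments are needed, because the 3-monthly and end-of-treatment marrows are already scheduled. Transplant is not a listed discontinuation reason in Protocol 7.1.5, so it has to be derived and may be incomplete. The added figure will probably be less favourable. It is also post hoc, because the current SAP entry (09-Nov-2021) already postdates database lock.
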